## KM Analysis

KM analysis will be used to estimate the time from the date of index procedure to the date of death and to determine the overall participant survival rate at 1-, 3-, 6-, and 12-months. Catheter-related death is considered as the event.

Subjects that have not reached catheter-related death (event) will be censored or considered event free as described below.

- If the subject has experienced following events, subject will be censored at the earliest date of those events.
  - Catheter has been removed due to Kidney Transplant, Transferred to AVG/AVF, Peritoneal Dialysis, Withdrawal of Care, or Other reasons
  - Subject has discontinued from the study.

Note: How to assess the above events has been described in **Error! Reference source not found.**the Binary Analysis section.

- All the other subjects will be considered event free and will be censored on visit day (visit day can vary from lower limit to upper limit of visit window).

This endpoint will be evaluated on the mITT population through 1-month, 3-months, 6-months, and 12-months.

### 5.3.5 Overall Catheter Survival Rate at 1-month, 3-months, 6-months, and 12-months post-index procedure, defined as the proportion of Pristine™ Catheters that have not been removed for any cause.

#### Binary Analysis

Subject will be considered as a failure of the endpoint for a given visit if the subject has the catheter removed due to infection or catheter dysfunction prior to the upper limit of visit window for the visit:

- **Hemodialysis Catheter Re-interventions CRF Page:** Date of Re-Intervention: <= upper limit of the visit window AND Reason for catheter removal: Equals Infection/Catheter Dysfunction); subject will be considered as a failure at the re-intervention date

If the subject has not become failure and experience one of the following events prior to the lower limit of visit window, then subject will be considered as non-evaluable at the earliest occurrence of following event dates.

- Catheter has been removed due to Kidney Transplant, Transferred to AVG/AVF, Peritoneal Dialysis, Withdrawal of Care, or Other reasons
  - *Hemodialysis Catheter Re-Interventions CRF page: Catheter removal Equals Yes AND Reason for catheter removal Equals: Kidney Transplant, Transferred to AVG/AVF, Peritoneal Dialysis, Withdrawal of Care, or Other*

OR

- Subject has discontinued from the study.

If the subject has experienced any of the above **non-evaluable** events prior to the lower limit of visit window subject will be counted as a non-evaluable for a given visit. Else subject will be considered as a success of the endpoint for a given visit.

The overall catheter survival rate will be reported with 95% confidence interval from the exact binomial method. The analysis will be performed on the mITT population through 1-month, 3-months, 6-months, and 12-months.

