3.2 Secondary Endpoints

The following secondary endpoints will be evaluated using descriptive statistics to provide further information related to the safety and performance of the Pristine™ Long-Term Hemodialysis Catheter. All secondary endpoints will be summarized with descriptive statistics.

- *Rate of freedom from catheter-related bloodstream infection (CRBSI)*, defined by 2019 KDOQI Guidelines for CRBSI through 1-month, 3-months, 6-months, and 12 months post-index procedure.

- *Rate of freedom from Device and/or Procedure-related adverse events*, at 1-month, 3-months, 6-months, and 12 months post-index procedure.
- *Rate of Technical Success*, defined as the successful placement of the Pristine™ Long-Term Hemodialysis Catheter, as assessed by the Investigator during the Index Procedure.
- *Overall Participant Survival Rate* at 1-month, 3-months, 6-months, and 12 months post-index procedure, defined as the proportion of participants that have not died from any catheter related complication.
- *Overall Catheter Survival Rate* at 1-month, 3-months, 6-months, and 12 months post-index procedure, defined as the proportion of Pristine™ Catheters that have not been removed for any cause.
- *Overall Patency Rate*, at 1-month, 3-month, 6-months, and 12-months post-index procedure, defined as the Pristine™ catheter having the ability to achieve a mean dialysis blood flow of $\geq 300\text{mL/min}$ without need for additional interventions.^{5,6}

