4.4 End of Study Definition

A participant is considered to have completed the study upon conclusion of the 12-Month (± 1 month) follow-up visit. The end of the study is defined as the date of the last visit of the last participant in the study.

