16 APPENDICES

Appendix A - Study Definitions

Appendix B - IFU

16.1 Appendix A - Definitions

Term	Definition
Access Censoring Events	Include participant transfer to Peripheral dialysis, kidney transplantation, AVF, AVG, or the event of a participants premature discontinuation in the investigation due to withdrawn consent, withdrawal by PI, LTF, or participant death (refer to abbreviations for definitions).
Active Participant	An investigation participant who has not completed all required investigation follow-up and who has not prematurely discontinued participation in this clinical investigation (refer to Section 6.5) at the timepoint of reference.
Adjunctive Procedure	Procedure(s) completed during the index procedure (prior to leaving the procedure room) as part of SOC procedures. Procedures to ensure HD continuity, as well as procedures to address AEs.
Adverse Device Effect (ADE)	An ADE is an AE that is considered to be related to the use of the Pristine™ Catheter. This includes AEs resulting from insufficient or inadequate IFU, operation, or any malfunction of the Pristine™ Catheter. Additionally, this definition includes any event resulting from use error or from intentional misuse of the Pristine™ Catheter.
Adverse event (AE)	
An AE is defined as any untoward medical occurrence, unintended disease or injury, or untoward clinical signs (including abnormal laboratory findings) in participants, users, or other persons, whether or not related to the Pristine™ Catheter and whether anticipated or unanticipated. For users or other persons, this definition is restricted to events related to the use of the Pristine™ Catheter.
 
Note: Pre-existing conditions should be considered as part of the participant's medical history and should not be reported as an AE unless there is a substantial increase in severity or frequency of the condition, which has not been attributed to natural history.
 
Exacerbation of an existing condition should be reported as an AE if the event meets the CIP definition of an AE.

All Interventions [Post Creation / After First Use]	The number of interventions [post creation / after first use] inclusive of all interventions (facilitation, maintenance, and HD continuity interventions).

Term	Definition

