### 5.3 Secondary endpoints

#### 5.3.1 Rate of freedom from catheter-related bloodstream infection (CRBSI) defined by 2019 KDOQI Guidelines for CRBSI.

##### Binary Analysis

Subject will be considered as having CRBSI for a given visit if the subject has experienced device-related bloodstream infection prior to the upper limit of visit window for the visit:

- **AE CRF Page:** AE start date  $\leq$  upper limit of the visit window AND Relationship to study Device: Equals 'Related' or 'Likely Related' AND Was event infectious: Equals Yes AND Select Type of Infection: Equals Blood Stream and Were there clinical manifestation and at least 1 positive blood culture with no apparent source: Equals Yes; subject will be considered as a failure at the AE date

If the subject has not become failure and experience one of the following events prior to the lower limit of visit window, then subject will be considered as non-evaluable at the earliest occurrence of following event dates.

- Catheter has been removed due to Kidney Transplant, Transferred to AVG/AVF, Peritoneal Dialysis, Withdrawal of Care, or Other reasons

***Hemodialysis Catheter Re-Interventions CRF page:*** Catheter removal Equals Yes AND Reason for

*catheter removal Equals: Kidney Transplant, Transferred to AVG/AVF, Peritoneal Dialysis, Withdrawal of Care, or Other*

OR

- Subject has discontinued from the study.

Else subject will be considered as a success (freedom from CRBSI) for a given visit.

The rate of freedom from CRBSI will be reported with 95% confidence interval from the exact binomial method. The analysis will be performed on the mITT population through 1-month, 3-months, 6-months, and 12-months.

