## KM Analysis

KM analysis will be used to estimate the time from the date of index procedure to the date of catheter removal due to infection or catheter dysfunction and to determine the overall catheter survival rate at 1-, 3-, 6-, and 12-months. Catheter removal due to infection or catheter dysfunction is considered as the event.

Subjects that have not reached catheter removal due to infection or catheter dysfunction (event) will be censored or considered event free as described below.

- If the subject has experienced following events, subject will be censored at the earliest date of those events.
  - Catheter has been removed due to Kidney Transplant, Transferred to AVG/AVF, Peritoneal Dialysis, Withdrawal of Care, or Other reasons
  - Subject has discontinued from the study.

Note: How to assess the above events has been described in **Error! Reference source not found.**the Binary Analysis section.

- All the other subjects will be considered event free and will be censored on visit day (visit day can vary from lower limit to upper limit of visit window).

This endpoint will be evaluated on the mITT population through 1-month, 3-months, 6-months, and 12-months.

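### Overall Catheter Survival (SAP 5.3.5) is defined as not removed for any cause, but both its analyses count only removals for infection or catheter dysfunction

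*SAP*

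**What the plan says.** Protocol 3.2 describes Overall Catheter Survival at 1, 3, 6 and 12 months as "defined as the proportion of Pristine™ Catheters that have not been removed for any cause". SAP 2.7.2 and the heading of SAP 5.3.5 repeat that definition.

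The rules under that heading are narrower:

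- **Binary failure.** The subject fails at a visit if the subject "has the catheter removed due to infection or catheter dysfunction prior to the upper limit of visit window".
- **Binary non-evaluable.** A subject leaves the denominator under the clause that begins "If the subject has not become failure and experience one of the following events prior to the lower limit of visit window". One listed event is study discontinuation. The other is "Catheter has been removed due to Kidney Transplant, Transferred to AVG/AVF, Peritoneal Dialysis, Withdrawal of Care, or Other reasons".
- **Binary default.** For everyone left over: "Else subject will be considered as a success of the endpoint for a given visit".
- **KM.** "Catheter removal due to infection or catheter dysfunction is considered as the event". The other listed removals, and discontinuations, are censored at their date.

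Protocol Appendix A defines Access Censoring Events. These "Include participant transfer to Peripheral dialysis, kidney transplantation, AVF, AVG", together with premature discontinuation. The entry does not say which endpoints it governs.

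Protocol 10.6 makes the secondary endpoints descriptive, with no hypothesis test. Protocol section 3 and SAP 1.2 say that study information is intended for the device's labeling.

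**The concern.** A removal for transplant, new access, change of modality, withdrawal of care or another reason is still a removal. Under the stated definition it is a failure. Under the SAP's rules it never is: it leaves the denominator, is censored, or, if it falls between the lower and upper window limits, passes through the default and is scored as a surviving catheter.

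The same removal list and default serve the other secondary endpoints, such as bloodstream infection in SAP 5.3.1. There a removal for another reason is not the endpoint's own event, so excluding or censoring it does not contradict the definition. In 5.3.5 it does.

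At stake is the meaning of a reported figure. A rate carrying the any-cause definition would omit whole classes of removal, and a reader of a report or label would take it as the proportion of catheters still in place.

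**Working it through.** **No stated figure to reproduce.** The documents give no expected rate, precision target or power for this endpoint. The check therefore covers direction, then size under assumed rates.

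**1. Direction, binary.** Split the subjects at one visit into:
- F: removed for infection or dysfunction
- O: removed for another reason before the window opens
- W: removed for another reason inside the window
- D: discontinued with the catheter in place
- S: catheter still in place

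SAP rate = (S + W)/(S + W + F).
Any-cause rate, with D also non-evaluable = S/(S + W + F + O).

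The SAP numerator is never smaller and its denominator never larger, so the SAP rate is equal or higher. A check over 320,532 splits of 142 subjects found no exception.

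Counts for illustration, with N = 142 (planned size) and D = 21 (the plan's 15% attrition through 90 days); F, O and W are assumed:

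| F | O | W | S | SAP | Any cause |
|---|---|---|---|---|---|
| 14 | 0 | 0 | 107 | 107/121 = 88.4% | 107/121 = 88.4% |
| 10 | 10 | 0 | 101 | 101/111 = 91.0% | 101/121 = 83.5% |
| 14 | 28 | 0 | 79 | 79/93 = 84.9% | 79/121 = 65.3% |
| 14 | 28 | 4 | 75 | 79/93 = 84.9% | 75/121 = 62.0% |

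**2. Direction, KM.** With n subjects at risk at an event time, the SAP factor is 1 − dF/n and the any-cause factor is 1 − (dF + dO)/n. Both use the same risk set, because an other-reason removal ends follow-up either way. The SAP curve is therefore never lower. In 1,000 simulated cohorts at four time points there were no exceptions in 4,000 comparisons.

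**3. Size, KM.** Assume constant hazards, no other dropout, and net 12-month risks pf (infection or dysfunction) and pe (other reasons):

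hf = −ln(1 − pf)/365, he = −ln(1 − pe)/365, ht = hf + he.
SAP KM = exp(−hf·t); any-cause KM = exp(−ht·t).

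| pf / pe | 12 months: SAP vs any cause | Gap at t = 90 days |
|---|---|---|
| 5% / 5% | 95.0 vs 90.2 | 1.2 points |
| 10% / 20% | 90 vs 72 | 5.2 points |
| 10% / 30% | 90 vs 63 | 8.2 points |
| 15% / 40% | 85 vs 51 | 11.4 points |

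**4. Size, binary at 12 months.** The window is 365 ± 30 days (Protocol 7.5), so its lower limit is L = 335. Protocol 4.4 says: "A participant is considered to have completed the study upon conclusion of the 12-Month" visit. Observation can therefore end at any day U from 335 to 395.

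S = exp(−ht·U)
NE = (he/ht)(1 − exp(−ht·L)), non-evaluable
IW = (he/ht)(exp(−ht·L) − S), other-reason removal inside the window
SAP rate = (S + IW)/(1 − NE); any-cause rate = S.

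For 10%/30%, ht = 0.0012659 and he/ht = 0.772. NE = 0.772 × (1 − 0.6544) = 0.2668, or about 38 of 142 dropped.

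- U = 335: S = 0.6544, IW = 0. SAP = 0.6544/0.7332 = 89.3%, against 65.4%.
- U = 395: S = 0.6065, IW = 0.0369, or about 5 of 142 removed catheters scored as success. SAP = 0.6435/0.7332 = 87.8%, against 60.7%.

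If the in-window removals were instead non-evaluable, the U = 395 rate would be 0.6065/(0.7332 − 0.0369) = 87.1%. The success default thus adds 0 to 0.7 points here. The rest of the gap comes from the narrow event and the exclusions.

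**The case against.** **Device failure is a sensible endpoint, and censoring planned removals is common.** That stands as a design choice, but then the definition is wrong in three places. Access Censoring Events does not settle it: the entry is not tied to this endpoint, and it does not list removals for withdrawal of care or for other reasons.

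**A reader might infer that the reported rate can never fall below the stated definition.** That is too strong. Read literally, the definition could be a crude proportion of all subjects in which discontinued subjects count as not removed. With W = 0 the SAP rate falls below that proportion when D·F > S·O. For F = 30, O = 10, D = 50 and S = 52, the SAP gives 52/82 = 63.4% against (52 + 50)/142 = 71.8%. That reversal comes from the handling of discontinuation, not from which removals count. The one-way direction needs discontinuations handled alike.

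**A reader might take the success default as the main fault, or the larger gaps as forecasts.** Neither is supported. The default adds under one point in the 10%/30% illustration. The 20% to 40% other-reason risks are assumptions, and exclusion criterion 3 keeps out patients already awaiting fistula or graft maturation.

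**A reader might extend the point to patency in SAP 5.3.6.** That section expressly makes the same removals non-evaluable or censored, so the documents do not support it.

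**The removals are not hidden.** SAP 6.8 summarizes re-interventions and SAP 6.1 reports discontinuations by reason. This limits the harm but does not correct the labelled rate.

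**Conclusion.** The mismatch is explicit and nothing in the documents reconciles it. Carried out as written, SAP 5.3.5 reports freedom from removal for infection or dysfunction under an any-cause definition.

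Only the direction is firm, and it is conditional: with discontinuations handled the same way, the reported rate equals the any-cause rate when there are no other-reason removals and is otherwise generally higher. The size depends on removal rates that the documents do not give. Under constant hazards and no other dropout, the 12-month KM gap runs from about 5 points (5%/5%) to 34 points (15%/40%).

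The endpoint is secondary and descriptive, so the primary test, the sample size and the acceptance criterion are untouched. The labeling intent is the reason to correct it before analysis.

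**What to change.** **Preferred, because it matches the definition in both documents.** In the SAP 5.3.5 binary analysis, make removal for any reason, dated up to the upper window limit, the failure. In KM, make removal for any reason the event. Keep discontinuation or death with the catheter in place non-evaluable or censored, as now, and say so. Report the present rule as a separate line labelled *freedom from removal for infection or catheter dysfunction*.

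**Alternative, if device-failure survival was intended.** Correct the definition and label in Protocol 3.2, SAP 2.7.2 and SAP 5.3.5. Report any-cause survival alongside. Score in-window removals for other reasons as non-evaluable rather than success.

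**Cost.** SAP wording, derivation code and one extra table. The Re-Interventions CRF already records removal, date and reason, so no new data are needed. The alternative also needs a protocol wording change. The main downside is a lower headline catheter-survival figure.

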## KM Analysis

KM analysis will be used to estimate the time from the date of index procedure to the date of catheter removal due to infection or catheter dysfunction and to determine the overall catheter survival rate at 1-, 3-, 6-, and 12-months. Catheter removal due to infection or catheter dysfunction is considered as the event.

Subjects that have not reached catheter removal due to infection or catheter dysfunction (event) will be censored or considered event free as described below.

- If the subject has experienced following events, subject will be censored at the earliest date of those events.
  - Catheter has been removed due to Kidney Transplant, Transferred to AVG/AVF, Peritoneal Dialysis, Withdrawal of Care, or Other reasons
  - Subject has discontinued from the study.

Note: How to assess the above events has been described in **Error! Reference source not found.**the Binary Analysis section.

- All the other subjects will be considered event free and will be censored on visit day (visit day can vary from lower limit to upper limit of visit window).

This endpoint will be evaluated on the mITT population through 1-month, 3-months, 6-months, and 12-months.

### 5.3.6 Overall Patency Rate, at 1-month, 3-months, 6-months, and 12-months post-index

**procedure, defined as the Pristine™ catheter having the ability to achieve a mean dialysis blood flow of  $\geq 300\text{mL/min}$  without need for additional interventions**

### **Binary Analysis**

Subject will be considered as loss of overall patency if subject has experienced one of the following events:

- Subject undergoes re-intervention and re-intervention date is after the first dialysis session date
  - **Hemodialysis Catheter Re-Interventions CRF:** Date of Re-intervention > **Procedure Overview Details-Part 2 CRF:** Date of first dialysis session and subject will be considered as a failure at re-intervention date
- Subject has not been able to maintain the patency since last visit
  - **Most Recent Dialysis Session Blood Flow Rate CRF:** Was the catheter able to maintain patency since the last visit (Have the ability to achieve a mean dialysis blood flow of  $\geq 300\text{mL/min}$ )? No . The subject will be considered as a failure at Catheter Dysfunction Date

The subject will become a failure at the earlier occurrence of the above two events. If the subject has lost the overall patency prior to the upper limit of visit window subject will be counted as a failure for a given visit.

If the subject has not become failure and experience one of the following events prior to the lower limit of visit window, then subject will be considered as non-evaluable at the earliest occurrence of following event dates.

- Catheter has been removed due to Kidney Transplant, Transferred to AVG/AVF, Peritoneal Dialysis, Withdrawal of Care, or Other reasons  
*Hemodialysis Catheter Re-Interventions CRF page: Catheter removal Equals Yes AND Reason for catheter removal Equals: Kidney Transplant, Transferred to AVG/AVF, Peritoneal Dialysis, Withdrawal of Care, or Other*  
OR
- Subject has discontinued from the study.

If the subject has experienced any of the above **non-evaluable** events prior to the lower limit of visit window subject will be counted as a non-evaluable for a given visit; else subject will be considered as a success for a given visit.

The overall patency rate will be reported with 95% confidence interval from the exact binomial method. The analysis will be performed on the mITT population through 1-month, 3-months, 6-months, and 12-months.

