Possibly Related AE	An AE is possibly related if it is capable of being related but relatively unlikely or there is insufficient information to determine if the AE is related to the device or procedure.
Post Procedure Event	AE that occurred after the index procedure.
Principal Investigator	Qualified person responsible for conducting the clinical investigation at an investigation site. If a clinical investigation is conducted by a team of individuals at an investigation site, the PI is responsible for leading the team.
Procedure access Site	A site of incision access during index procedure.
Procedural Event	AE that occurred during the index procedure.
Procedure Duration	The duration of the index procedure as defined in this CIP.
Procedure Related AE	AEs directly attributable to the index procedure.
Procedure Success	Successful catheter creation using the Pristine™ Long-Term Hemodialysis Catheter with flow confirmed through the catheter.
Recruitment	Active efforts to identify participants who can be suitable for enrolment into the clinical investigation.
Re-interventions	Any additional procedures with the initial catheter after the index procedure.
Screen Failure	A participant who is excluded from this clinical investigation as based on the eligibility criteria.
Serious Adverse Device Effect (SADE)	ADE that has resulted in any of the consequences characteristic of a SAE.

Term	Definition
Serious Adverse Event	
An AE that led to any of the following:
 
 • Death; or • Serious deterioration in the health of the participant, users or other persons as defined by one or more of the following: 
 - A life-threatening illness or injury; or - A permanent impairment of a body structure or a body function including chronic diseases; or - In-patient or prolonged existing hospitalization; or - Medical or surgical intervention to prevent life-threatening illness or injury or permanent impairment to a body structure or a body function; or • Fetal distress, fetal death or a congenital abnormality or birth defect including physical or mental impairment. 
Note: Planned hospital visits and / or hospital stays, or procedures required by this CIP (including subsequent interventions assessed in the clinical investigation endpoints), without serious deterioration in health should not be considered SAEs.

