### **KM Analysis**

KM analysis will be used to estimate the time from the date of index procedure to the date of overall patency loss and to determine the overall patency rate at 1-, 3-, 6-, and 12-months. The loss of overall patency is considered as the event.

Subjects that have not reached overall patency loss (event) will be censored or considered event free as described below.

- If the subject has experienced following events, subject will be censored at the earliest date of those events.

- Catheter has been removed due to Kidney Transplant, Transferred to AVG/AVF, Peritoneal Dialysis, Withdrawal of Care, or Other reasons
- Subject has discontinued from the study.

Note: How to assess the above events has been described in **Error! Reference source not found.** the Binary Analysis section.

- All the other subjects will be considered event free and will be censored on visit day (visit day can vary from lower limit to upper limit of visit window).

This endpoint will be evaluated on the mITT population through 1-month, 3-months, 6-months, and 12-months.

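### The SAP 5.3.6 patency rule has no filter on reason, so catheter removals that the same section lists as non-evaluable or censored count as patency loss once dialysis has begun

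*SAP*

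**What the plan says.** Protocol 3.2 defines overall patency as the ability to reach a mean dialysis blood flow of at least 300 mL/min "without need for additional interventions", at four times after the index procedure. SAP 5.3.6 turns this into two failure limbs, and the earlier one counts:

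- Re-intervention limb: "Subject undergoes re-intervention and re-intervention date is after the first dialysis session date". The programming line compares the re-intervention date with the "Date of first dialysis session and subject will be considered as a failure at re-intervention date". It does not refer to the type of procedure or the reason for it.
- Flow limb: "Subject has not been able to maintain the patency since last visit", taken from the blood-flow CRF.

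A subject can also be non-evaluable. One ground is "Catheter has been removed due to Kidney Transplant, Transferred to AVG/AVF, Peritoneal Dialysis, Withdrawal of Care, or Other reasons", read from the Re-Interventions CRF. The other is discontinuation from the study. Both are conditional: "If the subject has not become failure and experience one of the following events prior to the lower limit of visit window". The Kaplan-Meier part has the same order, because only subjects without patency loss are censored. Its clock is set to "estimate the time from the date of index procedure to the date of overall patency loss".

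Three other places bear on this. SAP 5.2.1 takes the date of a removal for a listed reason from the re-intervention date on that same CRF. SAP 5.3.5 (catheter survival) does filter by reason and counts only removals for infection or catheter dysfunction as failures. Protocol Appendix A defines re-interventions as "Any additional procedures with the initial catheter after the index procedure".

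**The concern.** The re-intervention limb and the removal exemption read the same CRF page and the same date, and the failure limb is applied first. Once dialysis has started, a removal that should take the subject out of the denominator, or censor the subject, meets the failure condition on that same date. A working catheter taken out because a fistula is ready would be reported as having lost patency.

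This matters although no hypothesis is tested. Protocol 2.1 describes these catheters as a bridge to fistula maturation or a donor organ, so removals of this kind are to be expected over 12 months. Protocol 3 says that study information is intended for the device's labeling. A programmer would have either to follow the text and report a rate that contradicts the section's own exemption, or to choose an undocumented remedy once data are in hand.

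A smaller question concerns the start of counting. A re-intervention on or before the day of first dialysis does not meet the limb, yet time is measured from the index procedure.

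**Working it through.** The documents give no expected patency rate, removal rate or precision target for this endpoint, so there is no figure to reproduce. The check has two parts.

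**1. The rule applied literally.** Take first dialysis on day 2, and the 3-month window as 90 ± 15 days, that is days 75 to 105. Assume the flow question is never answered No.

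| Case | Re-intervention after first dialysis? | Result as written |
|---|---|---|
| Removal for AVF transfer, day 60 | Yes (60 > 2) | Failure; the exemption is not reached |
| Removal for AVF transfer, day 2 | No (2 = 2) | Non-evaluable |
| Study discontinuation, day 60, no re-intervention entry | Not applicable | Non-evaluable |
| Thrombolysis, day 2 | No (2 = 2) | Success |
| Thrombolysis, day 1, first dialysis moved to day 3 | No (1 < 3) | Success |

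Row 1 is the contradiction. Rows 2 and 3 mark its limits. The analysis set is mITT, and SAP 4.1 puts subjects whose device was inserted but who had no first dialysis in a separate group, so in practice row 2 leaves only same-day removals. Rows 4 and 5 show the start-of-counting question.

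**2. Size, by illustration only.** Let F be the true patency loss by a time point and E the proportion with a listed removal by then, each in the absence of the other. Assume independent exponential times, ignore discontinuation, and ignore the gap between the lower and upper window limits. N = 142 is the planned sample size.

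- Kaplan-Meier, listed removals censored: 1 − F.
- Kaplan-Meier and binary, literal rule: S = (1 − F)(1 − E).
- Binary, listed removals non-evaluable: S / (S + c). Here c is the proportion whose patency loss comes first: c = [ln(1 − F) / (ln(1 − F) + ln(1 − E))] × (1 − S).

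With F = 0.20 and E = 0.30:

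- S = 0.80 × 0.70 = 0.56.
- c = [0.223 / (0.223 + 0.357)] × 0.44 = 0.169.
- Kaplan-Meier: 80% censored against 56% literal, a difference of 24 points.
- Binary: 0.56 / (0.56 + 0.169) = 76.8% (about 80 of 104) against 56.0% (about 80 of 142), a difference of 20.8 points.

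Over F from 10% to 30% and E from 10% to 50%, the Kaplan-Meier understatement equals (1 − F) × E:

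- Smallest: 0.70 × 0.10 = 7 points (70% to 63%).
- Largest: 0.90 × 0.50 = 45 points (90% to 45%).
- The binary differences for the same two cases are 68.8 − 63.0 = 5.8 points and 86.1 − 45.0 = 41.1 points.

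Leaving out early re-interventions acts the other way, towards higher patency. Its size cannot be derived from the documents.

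**The case against.** The strongest reply is that the intent is plain. Both the binary and the Kaplan-Meier text name these removals as non-evaluable or censored, so a careful programmer could let the specific clause override the general one. The derived data specification in SAP Appendix 2, which is not reproduced in the public text, might hold the filter. The intent is indeed clear, and that is why this is an internal contradiction and not a disputed choice of estimand. But the rule as written, with its stated order, gives the opposite result, and a filter elsewhere would still leave the SAP body to be corrected.

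A reader might infer that censoring never operates for this endpoint. The documents do not support that: the discontinuation limb works for anyone without a qualifying re-intervention entry, and a removal on the day of first dialysis stays non-evaluable.

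A reader might also infer that counting from first dialysis is simply an error, so that the rate is shown to be wrong in both directions. That goes too far. Dialysis blood flow cannot be observed before a first session, mITT already separates out subjects without one, Protocol Appendix A recognises counting interventions after first use, and the flow limb can still catch an early problem that persists. What remains is a mismatch with the Kaplan-Meier origin and with the protocol's definition of re-interventions, which needs alignment or a justification.

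The removal rates are assumptions. The nearest figure in the documents is 15% attrition through 90 days (Protocol 10.2), which is not a removal rate, and exclusion criterion 3 bars patients already awaiting AVF or AVG maturation. Nothing in the documents supports a particular value such as 30% or 50%.

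**Conclusion.** The point stands for listed removals after first dialysis. As written, SAP 5.3.6 classes them as patency loss in both analyses, against its own exemption and out of line with the reason filter in SAP 5.3.5. The direction is certain: reported patency is too low whenever such a removal occurs in a subject with no earlier failure. The size is not known. The 80% against 56% (Kaplan-Meier) and 77% against 56% (binary) contrasts rest on assumed rates, independence and exponential times, and show only that the effect can be large if listed removals are common. The first-dialysis start is a separate and lesser matter of alignment, with an effect of opposite sign and unknown size.

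Patency is one of six secondary endpoints, summarised without hypothesis testing (Protocol 10.6). The primary test does not use this rule and is not affected. The correction should still be made before the 3-month report, where secondary endpoints are first summarised.

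**What to change.** 1. In the re-intervention limb of SAP 5.3.6, exclude catheter removals whose recorded reason is kidney transplant, AVG/AVF transfer, peritoneal dialysis, withdrawal of care or Other, since the SAP lists Other with the rest. Treat these as non-evaluable (binary) or censored on the removal date (Kaplan-Meier).
2. Keep all other re-interventions, and removals for infection or dysfunction, as failures. Restricting failure to procedures that restore function would narrow the protocol's definition, and it might need a CRF field for purpose that the documents do not show.
3. Either count re-interventions from the end of the index procedure, or state why counting starts at first dialysis and move the Kaplan-Meier origin to match.
4. Carry the same wording into the derived data specification.

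The cost is a short SAP revision and a programming change. Item 1 uses the removal indicator, reason and date already cited from the Re-Interventions CRF, so it needs no new data.
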